### 2.3 Exploratory Outcome Measures

- Change from baseline in selected biomarkers including but not limited to: YKL 40, PAI1, PDGF-BB, MCP-1, CCL-18, KL-6, CA-125, CA-19, Gal-3, MMP7 and collagen neoepitopes over time up to week 52 in all subjects.
- Time to initiation of pirfenidone or nintedanib treatment for SoC2 / Monotherapy subjects recruited to the original study design (prior to Protocol V6.0).
- Time to termination of pirfenidone or nintedanib treatment [b].
- Analysis of GAL-3 and IPF disease related genes of interest that might relate to the efficacy and/or safety of GB0139.

[b] Only for the SoC1 /Combination Population.

	Plus-Project Statistical Analysis Plan	
	Protocol Number: GALACTIC-1	Version: 1

## 2.4 Safety

The following measures of safety will be assessed throughout the study:

- Vital signs
- Physical examination
- Weight
- Clinical laboratory tests (haematology and clinical chemistry )
- Adverse events
- 12-lead electrocardiogram (ECG)

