2.2 Study Time and Events Schedule

Table 1: Study Time & Events Schedule

Visit	1	2	3	4	5	6	7	8	Withdrawal ⁹	Follow up ⁷
	Screening ¹	Baseline	Treatment							
Weeks of treatment		0	4	8	12	26	40	52	-	
Day Time window	6 weeks	0	29 ±3	57 ±3	85 ±3	183 ±7	281 ±7	365 ±7		7 days after final study visit (+7 days)
Informed consent	X									
HRCT sent to central review	X									
Demographics (including height, weight)	X									
Medical history	X									
Randomization		X								
In- /exclusion criteria	X	X								
Physical examination, vital signs	X	X	X	X	X	X	X	X	X	
HRQoL (SGRQ, SF-36)		X			X	X		X		
Dyspnoea index (UCSD-SOBQ)		X			X	X		X		
12-lead ECG	X	X	X	X	X	X		X	X	
Laboratory test (chemistry, haematology) ²	X	X	X	X	X	X	X	X	X	
Urinalysis	X		X	X	X	X	X	X	X	
Pregnancy test ^{3, 4}	X	X	X	X	X	X	X	X	X	
Biomarker sample		X	X		X	X		X		
Genetics sample ⁵		X								
Spirometry (FVC, FEV1)	X	X	X	X	X	X	X	X	X	
SpO ₂		X						X		
DLCO	X							X	X	
6MWT		X						X	X	
Administer 1st study medication (at clinic) & inhaler training ⁶		X								
Dispense trial drug		X	X	X	X	X	X			
Compliance / drug accountability ⁷			X	X	X	X	X	X	X	
Adverse events & conc. meds ⁸	X	X	X	X	X	X	X	X	X	X

Notes:

1. HRCT confirmation by central reading must be obtained as soon as possible following screening visit 1 and prior to visit 2
2. See [Table 2](#) and [Table 3](#) Section 10.4.9

3. In women of childbearing potential only: serum b-HCG will be required at visit 1 only, followed by urinary testing at subsequent visits.
4. This is optional and separate consent must be obtained. The sample can be taken at other study visits.
5. Subjects should be observed for 1 hour after the first dose to monitor for any acute adverse effects of study drug administration (e.g., bronchospasm – see Section 8.1)
6. Includes checking the subject's use of the DPI device (Plastiape monodose inhaler)
7. The follow-up will be performed via a phone call.
8. Events occurring prior to randomization and administration of drug are considered as pre-treatment (as defined in Section 11.1.1). Adverse events are also collected for up to the phone follow up.
9. FVC, DLCO and 6MWT will be performed as part of the withdrawal assessments.

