9.4 Safety Endpoints

- The following measure of safety will be assessing throughout the study:
 - Vital signs
 - Physical examination
 - Weight
 - Clinical laboratory tests (haematology, clinical chemistry and urinalysis)
 - Adverse events (see Section 11.0)
 - 12-lead electrocardiogram (ECG)

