10.4.9 Clinical Laboratory Evaluations

Clinical laboratory evaluations will be performed by a central laboratory as outlined below. Blood samples for analysis of the clinical chemistry and hematological parameters, urinalysis and biomarkers are shown in [Table 2](#), [Table 3](#) and [Table 4](#).

Table 2: Clinical Chemistry and Hematology Tests

Hematology	Serum Chemistry	
Hematocrit	Albumin	Glucose
Hemoglobin	Alkaline phosphatase (ALP)	Potassium
Leukocytes with differential count	Aspartate transaminase (AST)	Sodium
Platelet (count)	Alanine transaminase (ALT)	
	Bilirubin (total)	
	Calcium	
	Creatinine	

Table 3: Clinical Urinalysis Tests

Urinalysis		
	Bilirubin	pH
	Glucose	Protein
	Ketones	Specific gravity
	Leukocytes	Turbidity and color
	Nitrite	Urobilinogen
	Occult blood	

Results are recorded qualitatively as: -, +, ++, +++

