14.5.2 Safety Analysis

The primary assessment of benefit-risk of GB0139 3 mg compared to Plc will be based on efficacy and safety data over 52 weeks. All safety assessments described below will focus on

data collected within the first 52 weeks of the study. In addition, selected safety analyses will be repeated to include data collected beyond 52 weeks; further details will be specified in the SAP.

All treated subjects will be included in the safety analysis. The primary safety assessment will be based on the participants who received 3mg or placebo as study treatments. A separate safety assessment will be made for the participants who received study treatment in combination of nintedanib or pirfenadone. The particular tables and figures to be split in this way will be specified in the SAP. In general, safety analyses will be descriptive in nature. No hypothesis testing is planned.

Kaplan-Meier plots will be produced for the time to premature treatment discontinuation. Statistical analysis and reporting of adverse events will concentrate on treatment-emergent adverse events. All adverse events occurring between start of treatment and end of the residual effect period will be considered 'treatment-emergent'. The residual effect period is defined as the 28 days after the date of the last dose of trial medication. Adverse events that start before first drug intake and deteriorate under treatment will also be considered 'treatment-emergent'. Frequency, severity, and causal relationship of adverse events will be tabulated by system organ class and preferred term after coding according to the current version of MedDRA.

Laboratory data will be analysed both quantitatively as well as qualitatively. The latter will be done via comparison of laboratory data to their reference ranges. Values outside the reference range as well as values defined as clinically relevant will be highlighted in the listings. Treatment groups will be compared descriptively with regard to distribution parameters as well as with regard to frequency and percentage of subjects with abnormal values or clinically relevant abnormal values.

Vital signs, physical examinations, or other safety-relevant data observed at screening, baseline, during the course of the treatment and at the end-of-treatment evaluation will be assessed with regard to possible changes compared to findings before start of treatment.

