### 7.3.4 Laboratory Data

Système International (SI) units provided by a central laboratory will be used for presenting all laboratory values.

Values below the lower limit of quantification (LLOQ) will be replaced by the value of the LLOQ.

The hematology and clinical chemistry parameters to be summarized are as follows:

- Hematology: Hematocrit, Hemoglobin, Leukocytes with differential count, Platelet (count)
- Clinical chemistry: Albumin, Alkaline phosphatase (ALP), Aspartate aminotransferase (AST), Alanine aminotransferase (ALT), Bilirubin (total), Calcium, Creatinine, Glucose, Potassium, Sodium

The values provided by the central laboratory in standard units as well as the flags for Low/Normal/High (L/N/H) values relative to the normal range or Normal/Abnormal classifications will be used for summaries.

	Plus-Project Statistical Analysis Plan	
	Protocol Number: GALACTIC-1	Version: 1

For the continuous parameters, the results and the change from baseline (for post baseline assessments) will be summarized by treatment and visit. This summary will be repeated in the SoC1 / Combination and SoC2 / Monotherapy Populations.

For any categorical parameters (including incidence of abnormalities), the results will be summarized by treatment and visit based on the number of subjects with non-missing data at the visit as the denominator.

Separate subject listings of abnormalities across all populations, sorted by SoC, will be presented showing all data within the abnormal parameter over the study for the respective subject.

All laboratory results will be listed, including all unscheduled visits.

Serum pregnancy results (at screening) and urinary pregnancy results (post-screening) will be listed per subject and visit.

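### The SAP omits urinalysis, a protocol safety endpoint, from its safety measures and named laboratory summaries without declaring it, so no by-arm summary is explicitly specified

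*SAP*

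**What the plan says.** Protocol Section 9.4 gives six kinds of safety measure. The laboratory entry reads "Clinical laboratory tests (haematology, clinical chemistry and urinalysis". Protocol Section 2.2, Table 1, schedules urine testing at screening, at every treatment visit from Week 4 to Week 52, and at withdrawal. Table 3 in Section 10.4.9 lists eleven urine tests, including protein and occult blood, with the note "Results are recorded qualitatively as" negative to three plus. On analysis, Protocol Section 14.5.2 says of laboratory data: "Treatment groups will be compared descriptively with regard to distribution parameters as well as with regard to frequency and percentage of subjects with abnormal values".

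SAP Section 2.4 carries over the same six measures in the same order, but its laboratory entry is "Clinical laboratory tests (haematology and clinical chemistry". SAP Section 7.3.4 introduces its list with "The hematology and clinical chemistry parameters to be summarized are as follows" and then names blood tests only. It goes on to say "For any categorical parameters (including incidence of abnormalities), the results will be summarized by treatment and visit", and it provides for every laboratory result to be listed by subject. The SAP's own schedule in Section 11.2 still has a urinalysis row. SAP Section 9, on changes from the protocol, does not mention urine testing.

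**The concern.** A named safety endpoint is collected repeatedly, yet the analysis plan drops it from both places where a programmer would look to decide which tables to build. The SAP does not say that this is intended. Section 9 records a change as small as replacing a likelihood-ratio test with a Wald test in the logistic regressions, so its silence here looks like an oversight.

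At stake is the comparison between 3 mg and placebo of lower-grade urine changes. Protein and occult blood in urine are measured in no other planned laboratory panel, and summarising serum creatinine does not replace them. If no table is built, a modest imbalance in such changes would have to be found by reading individual listings.

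**Working it through.** No power or error-rate figure bears on this point. The check sets the two documents side by side and counts entries.

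| Item | Protocol | SAP |
|---|---|---|
| Laboratory safety measures | Haematology, chemistry, urinalysis (Section 9.4) | Haematology, chemistry (Section 2.4) |
| Haematology entries | 4 (Table 2) | 4 (Section 7.3.4) |
| Chemistry entries | 10 (Table 2) | 10 (Section 7.3.4) |
| Urine entries | 11 (Table 3) | 0 (Section 7.3.4) |
| Urinalysis visits scheduled | Screening + Weeks 4, 8, 12, 26, 40, 52 = 7, plus withdrawal (Table 1) | Screening + Weeks 8, 12, 26, 40, 52 = 6, plus withdrawal (Section 11.2) |
| Change declared | n/a | None in Section 9 |

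**Scope of the list.** The SAP's 4 + 10 = 14 named entries reproduce protocol Table 2 in full and take nothing from Table 3. The omission therefore covers the whole urine panel.

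**Whether the protocol's comparison covers urine.** Section 14.5.2 speaks of laboratory data without naming panels. Section 9.4 places urinalysis within clinical laboratory tests, so the natural reading includes it.

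**Amount of data.** The planned maximum of post-baseline panels, taking about 141 participants and ignoring dropout, death and withdrawal visits, is:

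- protocol schedule: 141 × 6 = 846 panels;
- SAP schedule: 141 × 5 = 705 panels.

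Both are upper bounds. Neither document gives an expected rate of abnormal urine results, so the size cannot be expressed as a signal missed.

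**Baseline.** Table 1 has no urinalysis at the baseline visit. Under SAP Section 5.3, baseline is the last value on or before Study Day 1, so the screening sample would normally serve. A change from baseline can be derived without new data.

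**The case against.** A reader might infer that the arms will never be compared on urine findings and that no planned table could show an imbalance. The documents do not support that, for two reasons.

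First, two general sentences could reach urinalysis. One is the sentence in SAP Section 7.3.4 on categorical parameters: every blood test named there is quantitative, while urinalysis is the panel the protocol records in grades. The other is a line below the visit-window table in SAP Section 5.2, saying that all collected safety data go into summaries. Both have some force, but neither names urinalysis. The first follows an explicit list without urine items, and the low/normal/high flags described just before it give it content without urine. The second sits among visit-window rules. The result is an ambiguity.

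Second, Protocol Sections 11.1.3 and 11.2 make a clinically significant laboratory change an adverse event, and SAP Section 7.3.2 tabulates treatment-emergent events by arm. Clinically relevant proteinuria or haematuria should therefore be visible there. This stands, and it limits the gap to changes not judged clinically relevant.

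There is also a version caveat. The SAP was written from protocol version 7.0, whereas the protocol text available here describes its design by reference to version 6.1_UK and cannot be confirmed as version 7.0. The schedules also differ on pregnancy testing, so the SAP may have copied a different schedule. Against this, the SAP schedule keeps the urinalysis row, and its note 2 still points to Table 3 in protocol Section 10.4.9, which in the available text is the urinalysis table. This supports the view that the endpoint was kept but does not prove it.

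**Conclusion.** The discrepancy is real and minor. The protocol makes urinalysis a safety endpoint and plans a descriptive comparison of abnormal laboratory values. SAP Sections 2.4 and 7.3.4 leave urinalysis out, and Section 9 does not say so. No by-arm urinalysis summary is explicitly specified. Findings not reported as adverse events could be confined to listings, depending on how the general sentences are read.

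The protocol plans no hypothesis tests for safety, so a descriptive table is at risk rather than a test. No efficacy conclusion depends on it, and nothing in the documents suggests an actual imbalance in urine findings. The verdict rests on the assumption that protocol version 7.0 kept urinalysis as a safety endpoint.

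**What to change.** 1. Add urinalysis to the laboratory entry in SAP Section 2.4 and to the parameter list in Section 7.3.4.
2. Specify the number and percentage of participants with an abnormal result, by arm and visit.
3. For the tests suited to negative-to-three-plus grading, such as protein, occult blood and glucose, add a shift table from screening to worst post-baseline grade. Summarise pH, specific gravity, and turbidity and color separately, as suits their type, because that scale does not fit them.
4. If the sponsor prefers listings only, declare and justify this in SAP Section 9.
5. Reconcile the Week 4 urinalysis entry, which is marked in protocol Table 1 and absent from SAP Section 11.2.

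The cost is a short SAP revision before database lock and a few descriptive tables from data already being collected. The tables need no extra site work.

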## 3. STUDY DESIGN

Full details of the study design can be found in the CSP Section 6.

### 3.1 Sample Size Determination

In the original design, the planned 150 subjects per arm (randomized 1:1:1 to the 3 treatment arms) provided approximately 87% power to detect a true mean difference of 100 ml between treatment arms in the FVC decline at Week 52, assuming a between subject standard deviation of 280ml, based on a two-sided 5% significance level.

For the updated design, the randomization ratio was changed to 2:1 (GB0139 3mg: Placebo). To detect a difference from placebo in the decline of FVC of 100ml with a standard deviation of 240ml at the significance level of 10%, a sample size of 141 would give 75% power. The lower standard deviation in the updated design was based on a blinded review of the data.

### 3.2 Randomization and Blinding

In the original design, within each SoC subpopulation (SoC1: subjects on nintedanib/pirfenidone at baseline, SoC2: subjects not treated with nintedanib/pirfenidone), subjects were randomized in blocks to double-blind treatment in a 1:1:1 ratio (GB0139 3 mg: GB0139 10 mg: Placebo).

For the updated design, there is no stratification and subjects are randomized in a 2:1 ratio GB0139 3mg: Placebo. The unbalanced randomization is to maintain the same probability of allocation to placebo post design change, since it is considered that this may facilitate participant enrollment.

The Sponsor arranged for the randomization and the packaging and labelling of trial medication. The randomization list will be generated using a validated system, which involves a pseudo-random number generator so that the resulting treatment will be both

	Plus-Project Statistical Analysis Plan	
	Protocol Number: GALACTIC-1	Version: 1

reproducible and non-predictable. The block size will be documented in the Clinical Study Report (CSR). Access to the codes will be controlled and documented.

This study is a double-blind study which will be maintained throughout the study, including the follow up period. The only exception to this is at the point of the design change, when the 10mg group in the SoC2 stratum had to be unblinded in order to withdraw them from the study early. Study medication is identified by a medication code number. Packaging and labelling will be otherwise identical. An Integrated Web Response System (IWRS) will be used to assign subjects to treatment groups at study start. The randomization code will be kept undisclosed up to database lock.

Other than designated unblinded team members at Syneos Health to support DSMB review, all subjects, Investigators and everyone involved in analyzing or with an interest in this double-blind study (Sites, Study team, Plus-Project, other service providers) will remain blinded to the randomized treatment assignments from both the original and the updated design until after database lock. A team from Syneos Health Biostatistics will have access to unblinded information to perform analyses for the DSMB (using controlled restricted folder access). DSMB members will receive outputs using coded treatments, so that summaries are separated by treatment, but it cannot be deduced which treatment code represents which treatment. The DSMB will have the option to request direct unblinding information at any point in line with the DSMB charter.

#### **4. ANALYSIS SETS**

In accordance with International Conference on Harmonisation (ICH) E3 [3] and E9 [4] guidelines, the analysis sets are defined as follows:

##### **4.1 Screened Set**

The Screened Set will include all subjects who provide informed consent for the study. This set will be used for subject listings and summaries of subject disposition.

##### **4.2 Intention-to-treat (ITT) Set**

All randomized subjects regardless of treatment received. Subjects will be analyzed based on the treatment to which they were randomized. The ITT set will be used for presentation of subjects in listings of demographic data and efficacy data.

##### **4.3 Modified ITT (mITT) Set**

This will comprise all randomized subjects who have had at least one dose of trial medication. Again, the subjects in this set will be analyzed according to the treatment to which they were randomized. The mITT set will be used for analysis of efficacy and biomarker endpoints and will be the primary analysis set of the study used for the primary and key secondary endpoints.

	Plus-Project Statistical Analysis Plan	
	Protocol Number: GALACTIC-1	Version: 1

#### **4.4 Safety Analysis Set (SS)**

All subjects who have had at least one dose of trial treatment will be analyzed for safety.

For all safety summaries, subjects with at least one dose of GB0139 or Placebo will be analyzed according to the first study treatment they received.

#### **4.5 Per Protocol Set (PPS)**

The PPS is a subset of the mITT set consisting of subjects who complied with the protocol sufficiently to ensure that these data would be likely to represent the effects of study intervention according to the underlying scientific model (e.g., subjects with at least 80% treatment compliance as defined in Section 7.3.1). It is used for efficacy sensitivity analyses and will only apply to the Primary Population.

It consists of all randomized and dosed subjects who meet key inclusion/exclusion criteria, only received the treatment they were randomized to, and did not have protocol deviations that were considered to impact efficacy. Subjects recruited under the original study design and who started nintedanib or pirfenidone whilst still on randomized treatment and prior to 52 weeks (i.e., in combination with study treatment) will be excluded from the PP Set. The following list of criteria will be used to exclude subjects from the Primary Population:-

- Not in Primary Population
- HRCT not done
- Treatment compliance not 80-120%
- FVC (%pred)  $\leq 45\%$  at Baseline
- DLCO (corrected for Hb)  $< 30\%$  or  $> 79\%$  of predicted at Baseline
- FEV1/FVC  $< 0.7$  at Baseline
- Use of nintedanib or pirfenidone during study

The final classification of protocol deviations relative to Week 52 will be made during a blinded data review prior to DBL, and all decisions, including exclusions from the PP Analysis Set, will be made blinded to study treatment.

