7.2 Exclusion Criteria

Subjects meeting any of the following exclusion criteria are not to be enrolled in the study/randomized to treatment:

1. Currently has significant airways obstruction: FEV1/FVC ratio of < 0.7 at screening.
2. Has clinical evidence of active infection, including, but not limited to, bronchitis, pneumonia, sinusitis, urinary tract infection, and cellulitis.
3. Has a history of malignancy within the last 2 years with the exception of basal cell carcinoma, squamous cell carcinoma of the skin (localised, treated or cured), chronic lymphocytic leukaemia (under observation) and prostate cancer requiring anti-androgens, localised treatment (minor surgery, radiotherapy) and/or managed by observation.
4. Has any condition other than IPF that, in the opinion of the investigator, is likely to result in the death of the subject within the next 2 years.

5. Presence of other disease that may interfere with testing procedures or in the judgement of the Investigator may interfere with trial participation or may put the patient at risk when participating in this trial.
6. Is likely to receive lung transplantation within the next 12 months.
7. Currently receiving nintedanib, pirfenidone, high dose corticosteroid, cytotoxic (e.g., chlorambucil, azathioprine, cyclophosphamide, methotrexate), vasodilator therapy for pulmonary hypertension (e.g., bosentan), also see prohibited medications (Section 8.3.2). A current dose of less than or equal to 15 mg/day of prednisone or its equivalent is acceptable if the dose is anticipated to remain stable during the study.
8. Prior use of GB0139 or previously randomized in GALACTIC-1.
9. Prior use of nintedanib or pirfenidone within 7 days of initiation of screening.
10. Prior use of investigational drugs within 30 days (or 5 half-lives, whichever is longer) of initiation of screening.
11. Participating in another interventional clinical trial.
12. Has a history of unstable or deteriorating cardiac or pulmonary disease (other than IPF) within the previous six months, including, but not limited to, the following:
 - a. Unstable angina pectoris or myocardial infarction, or percutaneous coronary intervention within the last 6 months.
 - b. Congestive heart failure requiring hospitalization.
 - c. Uncontrolled clinically significant arrhythmias.

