8.3 Prohibited Medications including approved and non-approved medications for IPF

8.3.1 Medications approved for IPF

- Nintedanib
- Pirfenidone

Following the most recent DSMB recommendation, the above approved medications for IPF are prohibited in GALACTIC-1, and if taken, should result in immediate exclusion from screening for the study, or withdrawal from the study treatment.

Under caring physician's medical judgement, if deemed appropriate, patients with IPF may discontinue nintedanib or pirfenidone and be considered for screening after a wash out period of minimum 7 days.

Following randomization, study participants are only permitted to take nintedanib or pirfenidone after withdrawals of the inhaled study treatment.

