14.6 Determination of Sample Size

The null hypothesis for the treatment difference between GB0139 at 3 mg and placebo for the two doses is tested using a type I error of 10% for a 2-side test. The power for detecting a statistically significant difference in the treatment effect (annual rate of decline in FVC or the FVC change from baseline to 52 weeks) is dependent on the effect size (mean treatment difference/ standard deviation) and the number of subjects per treatment group.

To detect an average difference from placebo in decline in FVC of at least 100 ml and with a standard deviation of 240 ml then a final sample size of 141 subjects would provide 75% power, assuming that future subjects are randomised into the study on a 1:2 randomisation allocation so that for every subject randomised to placebo 2 subjects will be randomised to 3 mg GB0139.

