### 5.3 Description of Baseline

For all treatment groups and under both designs, the baseline is defined as the last available, non-missing, value before or on Study Day 1. Study Day 1 is defined as the day of dosing (or the day of randomization for subjects randomized and not dosed).

At Week X, absolute change from baseline will be defined as value at Week X – baseline value.

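### The per-protocol exclusion list in SAP 4.5 tests spirometry at a different visit from the entry criteria, does not capture an unconfirmed HRCT, and conflicts with its own prose on antifibrotic use

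*SAP*

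**What the plan says.** SAP 4.5 first describes the PPS in prose. It is a subset of the mITT set: randomised and dosed subjects who meet key inclusion and exclusion criteria, received only their allocated treatment, and had no protocol deviation judged to affect efficacy. The prose also removes subjects recruited under the original design who started nintedanib or pirfenidone while still on randomised treatment and before 52 weeks. A bullet list follows, introduced by "The following list of criteria will be used to exclude subjects from the Primary Population". The bullets at issue are:

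- FVC at or below 45% predicted, DLCO outside 30% to 79% predicted, and FEV1/FVC below 0.7, each timed at Baseline;
- HRCT not done;
- "Use of nintedanib or pirfenidone during study".

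The rules that these bullets stand for are elsewhere:

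- **Lung function.** Protocol 7.1 requires FVC above 45% predicted and DLCO of 30% to 79% predicted, both at screening. Protocol 7.2 excludes an "FEV1/FVC ratio of < 0.7 at screening". Under SAP 5.3, "the baseline is defined as the last available, non-missing, value before or on Study Day 1".
- **HRCT.** Protocol 7.1 makes eligibility subject to central reading. Note 1 to the schedule in Protocol 2.2 says "HRCT confirmation by central reading must be obtained as soon as possible following screening visit 1 and prior to visit 2". SAP 6.2 lists a Yes/No variable for whether HRCT confirmed the diagnosis.
- **Antifibrotics.** Protocol 8.3.1 says that "study participants are only permitted to take nintedanib or pirfenidone after withdrawals of the inhaled study treatment". Protocol 10.5 lets participants withdrawn from study treatment stay in the study and resume usual IPF care.

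**The concern.** The PPS is the planned sensitivity set for the primary and secondary endpoints (SAP 5). Its value lies in being the set that its definition describes. The prose points to the entry criteria, but the list, which is what a programmer would code, tests something else in two places and contradicts the prose in a third. SAP 4.5 does not say whether prose or list governs, or whether the list is exhaustive.

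Read alone, the spirometry bullets misclassify in both directions. A correctly enrolled subject just above a cut-off at screening is removed if the Visit 2 reading falls below it. A subject enrolled in error below a cut-off is not caught if Visit 2 reads higher. The HRCT bullet does not catch a scan that was read centrally and not confirmed. The antifibrotic bullet removes subjects whose only use came after study drug was stopped, whom the prose does not name. At stake is whether agreement or disagreement between the PPS and mITT results can be interpreted.

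**Working it through.** **1. The plan's own figure.** Inputs from SAP 3.1: difference 100 mL, "with a standard deviation of 240ml at the significance level of 10%, a sample size of 141 would give 75% power", allocation 2:1. Protocol 14.6 gives the sidedness: "tested using a type I error of 10% for a 2-side test". With 94 on 3 mg and 47 on placebo:

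- SE = 240 × √(1/94 + 1/47) = 42.9 mL
- Power = Φ(100/42.9 − 1.645) = Φ(0.687) = 75.4%

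The stated 75% is reproduced.

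**2. Which measurement each bullet uses.** The schedule in Protocol 2.2 has spirometry at screening and again at Visit 2. Screening lasts up to 6 weeks. DLCO is done at screening, Week 52 and withdrawal, but not at Visit 2.

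| Bullet | Entry rule timed at | Baseline under SAP 5.3 | Same measurement? |
|---|---|---|---|
| FVC % predicted | screening | normally Visit 2 | no |
| FEV1/FVC | screening | normally Visit 2 | no |
| DLCO | screening | screening (nothing later scheduled) | yes |

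The mismatch therefore concerns FVC and FEV1/FVC only.

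**3. Size of the visit mismatch.** The documents give no retest SD and no baseline distribution, so everything in this step is assumed. For one subject, the chance of crossing a cut-off c from a screening value x is Φ((c − x)/s), where s is the SD of the change from screening to Visit 2.

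- FVC, s = 2 to 4 points: from 46%, 31% to 40%; from 50%, 1% to 11%.
- FEV1/FVC, s = 0.01 to 0.03: from 0.72, 2% to 25%.
- Other direction: a subject randomised in error at 44% FVC passes the Baseline bullet with probability 31% to 40%.

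For the whole trial, two sets of assumptions were simulated:

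- **Set A:** screening FVC mean 75% to 80% (SD 15), ratio mean 0.80 (SD 0.05) or 0.82 (SD 0.06), and s as above. Lost on FVC: 0.18% to 0.82%, or 0.3 to 1.2 of 141. Lost on FEV1/FVC: 0.45% to 2.77%, or 0.6 to 3.9 of 141. Together about 1 to 5.
- **Set B:** true FVC mean 78% (SD 17), true ratio mean 0.80 (SD 0.06), independent reading error at each visit of SD 2 to 4 points and 0.015 to 0.03. Lost on either: 2.0% to 4.3%, or about 3 to 6 of 141.

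The combined range is roughly 1 to 6 of 141.

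**4. Effect on precision.** If 6 of 141 are lost evenly (90 and 45 left), SE = 240 × √(1/90 + 1/45) = 43.8 mL and power = Φ(100/43.8 − 1.645) = 73.8%, against 75.4% with all subjects. If 1 is lost, power is 75.1%.

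**5. HRCT.** Entry asks for a scan and for central confirmation before Visit 2. The bullet asks only whether the scan was done. The two differ for a subject whose scan was read and not confirmed. The documents give no count of such subjects.

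**6. Antifibrotic use.** The prose covers original-design subjects, use begun on study drug, before 52 weeks. The bullet has no limit on cohort, on treatment status or on time. The difference is mainly subjects who start after stopping study drug. The documents give no number for these either.

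**The case against.** The strongest reply is that the list does not stand alone. The prose already requires key entry criteria to be met, and SAP 4.5 and 4.6 have exclusions agreed at a blinded review. A subject without central confirmation fails inclusion criterion 1 and could be removed there. This stands in part. A reader might infer that the PPS will keep ineligible subjects; the documents do not support that as a firm conclusion, only that the bullets alone would miss them. The reply does not help in the other direction, because neither the prose nor the review is said to restore an eligible subject whom a bullet removes.

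Second, the last pre-dose value is a defensible choice, since criteria are rechecked at Visit 2, and selection on a pre-treatment reading is unrelated to arm. The point about bias stands. But the protocol times these particular criteria at screening, so the list does not test what the prose claims.

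Third, a per-protocol set is meant to exclude subjects who leave the assigned treatment. Protocol 14.3 gives as an example at least 80% of treatment for at least 80% of 52 weeks, which an early switcher would fail. This stands: the wider antifibrotic rule is not wrong in itself, and it is a rule on conduct, not on entry. A reader might also infer that the wider bullet biases the treatment difference by a calculable amount. The documents do not allow that. The relevant contrast is bullet against prose, not all starters against none; initiation rates are not given; and Protocol 4.1 says that these drugs roughly halve decline, so keeping starters also alters the difference.

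Fourth, the reference to the Primary Population in the list heading is a slip. The first bullet is non-membership of that population, and the section closes by speaking of the PP set. It should not be read as cutting the primary analysis.

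**Conclusion.** SAP 4.5 is inconsistent with the entry rules on the FVC and FEV1/FVC visit and on HRCT confirmation, and with itself on antifibrotic use. These conclusions rest on the text alone. The DLCO bullet works as written.

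The consequence is limited. About 1 to 6 of 141 correctly enrolled subjects would be dropped through visit timing, a range that rests wholly on assumed retest SDs and baseline distributions. That costs at most about 1.6 percentage points of power in the PPS (75.4% to 73.8%). The effects of the HRCT and antifibrotic wording cannot be sized from the documents. Only the PP sensitivity analyses are touched: SAP 4.3 makes mITT the primary analysis set for the primary and key secondary endpoints. The correction is worth making because it is almost free and lets the sensitivity set match its own definition.

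**What to change.** In SAP 4.5, before database lock and unblinding:

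1. Refer the FVC and FEV1/FVC bullets to the screening or re-screening value used for eligibility. Re-screening needs naming because Protocol 10.3.2 allows earlier lung function results to be carried forward within 12 weeks. The DLCO bullet may be reworded to match, with no practical effect.
2. Widen the HRCT bullet to cover a scan not done or IPF not confirmed by central reading.
3. Reconcile the antifibrotic bullet with the prose and state one rule, including how it treats use that begins after study drug is stopped. Either scope can be defended as a per-protocol choice; two at once cannot.
4. Head the list as exclusions from the PP Set, and say whether it is exhaustive or supplements the prose.

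The cost is a few lines of SAP text and the matching programming. Screening spirometry, the HRCT confirmation variable and antifibrotic dates are already collected, so no new data or protocol change is needed.
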